1.1 Synopsis

Protocol Title

A Phase 1b, open-label, boost-optimization study of an adenoviral- vector based oral norovirus vaccine (VXA-G1.1-NN) expressing GI.1 VP1 administered orally to healthy adult volunteers.

Study Rationale and Hypothesis

VXA-G1.1-NN is an E1/E3-deleted, replication-incompetent, adenovirus 5 (Ad5) vaccine vectors designed for use as an oral vaccine for the prevention of noroviral gastroenteritis caused by norovirus genogroups GI.1. The monovalent vaccine vector encodes the full-length of viral protein 1 (VP1) gene of Norwalk virus (Norovirus GI.1). The adjuvant consists of a double-stranded RNA Toll-like receptor 3 (TLR3) agonist which enhances immune induction to expressed antigen in the gut mucosa.

Noroviruses are a genetically diverse group of small, non-enveloped, single-stranded positive sense RNA viruses belonging to the Caliciviridae family (Bresee, 2002). Norovirus infections are a leading cause of sporadic and epidemic gastroenteritis across all age groups worldwide (Hoa Tran, 2013; de Graaf, 2016). There is an urgent public health need for rapid development of novel interventions to prevent the spread of this disease, including prophylactic measures, such as vaccines (Esposito, 2020).

A unique and advantageous immune response elicited by oral vaccination is the induction of antibodies derived from mucosal cells. Given that the mucosal route of immunization produces superior mucosal immunity compared to injected vaccines, it is hypothesized that VXA-G1.1-NN oral vaccine may enable higher degrees of mucosal protection against infection when compared to a parenteral immunization method.

VXA-G1.1-NN is designed to elicit both antibody and T cell responses, mucosally and systemically, to Norovirus GI.1 Norwalk VP1. Prior completed Phase 1 studies with the Vaxart Vector Adjuvant Antigen Standard Technology (VAASTTM) platform have demonstrated protective immunity to viruses, such as norovirus, influenza, and respiratory syncytial virus, with both systemic and mucosal immune responses against the antigen of choice (Kim, 2016; Kim, 2018; Liebowitz, 2020).

Clinical data is available from 3 Phase 1 studies (VXA- NVV-101, VXA-NVV-102, and VXA-NVV-103) which evaluated multiple single- and multi-dose ranging of the monovalent vaccine VXA-G1.1-NN in over 200 healthy young adult subjects (18 to 49 years old). These studies indicate that the vaccine was tolerated well and generated robust immune responses including systemic and mucosal antibodies as well as memory immunoglobulin A (IgA)/ immunoglobulin G (IgG). In addition to increase in serum blocking titer fifty assay (BT50) titers, vaccine recipients also developed mucosally primed VP1-specific circulating antibody secreting cells (ASCs), IgA⁺ memory B cells expressing gut-homing receptor (α 4 β 7), and fecal IgA, indicating substantial and local responses potentially relevant to prevent norovirus infection (Kim, 2018).

Over the past year, global efforts for the development of effective COVID-19 vaccines have been strongly reliant, among other technologies, on the use of adeno-associated viral vectors (AAV) (Callaway, 2020). AAV-based COVID-19 vaccines from AstraZeneca, Johnson & Johnson, and the Gamaleya Research Institute of Epidemiology and Microbiology have been granted emergency use authorization in many countries worldwide. Contextually, emerging evidence generated in clinical settings with the AstraZeneca COVID-19 vaccine (AZD1222) indicates that a 12-week interval between vaccine doses might significantly improve efficacy and immunogenicity of AAV-based vaccination strategies compared to a shorter 4- or 6-week dosing interval (Voysey et al., 2021; Hung and Poland, 2021). Specifically, subjects who received two vaccine doses with a dose interval of at least 12 weeks showed neutralizing and anti-SARS-CoV-2 spike IgG antibody responses more than two-fold higher than those who received the two-dose regimen at an interval of less than 6 weeks. Accordingly, AZD1222 vaccine efficacy increased from 55% (<6-week interval) to 81% with an interval of at least 12 weeks. In light of these findings, the current Phase 1b study VXA-NVV-105 is designed to assess the safety and immunogenicity of the VXA-G1.1-NN vaccine with a 2-dose vaccination schedule using different repeat-dosing intervals (4, 8, or 12 weeks apart) in healthy young adults (18 to 55 years old).

The current phase 1b, open-label, boost-optimization study objectives and endpoints for an adenoviral- vector based oral norovirus vaccine (VXA-G1.1-NN) expressing GI.1 VP1 administered orally to healthy adult volunteers is presented below.

Objectives	Endpoints
Primary	
 To evaluate the immunogenicity of VXA-G1.1-NN with repeat-dose administration at Day 1 and varying boost schedules (Week 4, 8 or 12 post initial dose) in healthy adults aged 18-55, inclusive 	 VP1 specific IgA ASC by enzyme-linked immunospot (ELISpot) Norovirus G1.1 histo-blood group antigen (HBGA) blocking antibodies (BT50) VP1 specific serum IgG by Mesoscale Discovery (MSD) assay
Secondary	
• To assess the safety and tolerability of VXA- G1.1-NN with repeat-dose administration at varying boost schedules (Week 4, 8 or 12) in healthy adults aged 18-55, inclusive	 Frequency, duration, and severity of solicited symptoms of reactogenicity (local, systemic) for 1 week following each dose of study drug Frequency, duration, and severity of unsolicited serious AEs (SAEs), AEs of special interest (AESIs) and New Onset of Chronic Illness (NOCIs) through each Study Period (4 weeks post each vaccination)

Objectives and Endpoints (Primary and Secondary)

Overall Design

This is an open-label study in healthy adult participants age 18-55 years old. The study will enroll 30 subjects to one of three treatment cohorts.

- Cohort 1: (4-week boost vaccination) 10 subjects will receive two doses of 1x10¹⁰ IU± 0.5 log at Day 1 and Week 4
- Cohort 2: (8-week boost vaccination) 10 subjects will receive two doses of 1×10^{10} IU± 0.5 log at Day 1 and Week 8
- Cohort 3: (12-week boost vaccination) 10 subjects will receive two doses of 1×10^{10} IU± 0.5 log at Day 1 and Week 12

The study will include a screening period, Study Period 1 (Day 1 to 4 weeks post initial vaccination), Study Period 2 (4 Weeks from second vaccination will be initiated at Week 4 for Cohort 1, Week 8 for Cohort 2 and Week 12 for Cohort 3), and a follow-up period of 6 months post second vaccination in each cohort. Study assessments will be conducted as shown in the Schedule of Activities (SoA) in Section 1.2 (Table 2). In addition, participants will be contacted by phone between site visits to monitor for safety as specified in the SoA.

After signing an informed consent, participants will undergo screening assessments to determine study eligibility within a 45-day screening period.

Eligible participants will be enrolled and receive their first dose of study vaccine on Day 1.

During the Active study period, participants will record any potential symptoms of reactogenicity daily for 1 week post each vaccination, administered on Day 1 and Week 4, 8 or 12, depending on cohort assignment, using a Solicited Symptom Diary. Participants will return to the site as specified in the SoA to have safety assessments and samples collected for evaluation of immunogenicity.

At the participant's second vaccination visit (Week 4, 8 or 12 depending on Cohort assignment) they will have pre-dose safety assessments to determine eligibility to continue with the second vaccination. Additionally, female participants of childbearing potential must have a negative pregnancy test before receiving their second vaccination. Participants deemed ineligible for the second vaccination due to acute illness or new medical condition may be re-assessed, and if the condition resolves, may have a delayed second vaccination within 1 week of their scheduled vaccination Visit (+7 days window from Week 4, 8 or 12 depending on Cohort assignment). Participants with a delayed second vaccination will follow the delayed schedule through the rest of their Active Period as specified in the SoA.

If a subject remains ineligible for the second vaccination, they will complete an Early Termination visit and then enter the scheduled follow-up period per Cohort assignment as outlined in the SoA (1.2).

All participants will enter the follow-up period 4 weeks after their last vaccination and will be monitored for SAEs including AESIs and NOCIs through End of Study. Participants will also have samples collected for evaluation of immunogenicity as specified in the SoA.

Intervention Group and Number of Participants

Group	Study Drug	Dose (IU ±0.5 log)	No. of Doses	Dosing Schedule	No. of Subjects
Cohort 1	VXA-G1.1-NN	1x10 ¹⁰	2	Day 1 & Week 4 ^a	10
Cohort 2	VXA-G1.1-NN	$1 x 10^{10}$	2	Day 1 & Week 8 ^a	10
Cohort 3	VXA-G1.1-NN	$1 x 10^{10}$	2	Day 1 & Week 12 ^a	10
	30				

Table 1Treatment Arm, Doses and Sample Size

^a Subjects not eligible for the second dose (within the 7-day dosing window) will immediately enter the follow-up period.

Study Duration for Each Participant

1 of each subject, study participation is expected to fast as follow	ast as follows:	pected to la	is ex	pation	partici	, study	subject	For each
--	-----------------	--------------	-------	--------	---------	---------	---------	----------

Study Period Cohort 1		Cohort 2	Cohort 3		
	(Day 1 and Week 4)	(Day 1 and Week 8)	(Day 1 and Week 12)		
Screening Period:	45 days	45 days	45 days		
Study Period 1:	4 weeks (Day 1 – Week 4)	4 weeks (Day 1 – Week 4)	4 weeks (Day 1 – Week 4)		
Study Period 2:	4 weeks (Week 4 – 8)	4 weeks (Week 8 – 12)	4 weeks (Week 12 – 16)		
Follow-Up Period:	6 months following boost	6 months following boost	6months following boost		
Total Duration	7 Months	8 Months	9 Months		

Safety Monitoring Committee (SMC): No

1.2 Schedule of Activities

Active Period										
	Screen	Study Per	tudy Period 1 – Cohorts 1, 2, 3							
				Stu	dy Period 2	– Cohort 1				
			Study Period 2 –					hort 2		
								Study	Period 2 – C	Cohort 3
	-45d to	Day 1	Day 8	Day 29	Day 36	Day 57	Day 64	Day 85	Day 92	Day 113
Study Day	-1 d	(Wk 0)	(Wk 1)	(Wk 4)	(Wk 5)	(Wk 8) /ET ¹	(Wk 9)	(Wk 12)/ET ²	(Wk 13)	(Wk16)/ET ³
Visit Window (days)		n/a	0	±2	0	±2	0	±2	0	±2
Informed consent	Х									
Inclusion/Exclusion	Х	Х		Х						
Demographics	Х									
Medical history	Х									
Stool for occult blood	Х									
Blood Sample (HBsAg, HCV, HIV)	Х									
Urine drug screen	Х									
Alcohol Testing	Х									
Pregnancy Test ^a	Х	Х		X ¹		X ²		X ³		
Physical examination	Х	Xb	Xb	Xb	Xb	X ^b	Xb	X ^b	Xb	Xb
Vital Signs	Х	Х	Х	X	Х	Х	Х	Х	Х	Х
Safety laboratory tests	Х	Xc	Х	X	Х	Х	Х	Х	Х	Х
Urinalysis	Х	Х	Х	Х	Х	Х	Х	Х	Х	Х
COVID vaccination status	Х									
Vaccination		Х		X ^{1, d,e}		X ^{,2, d,e}		X ^{3, d,e}		
Dispense Solicited Symptom Diary		X ^{1,2,3}		X^1		X^2		X ³		
Review & Collect Solicited			Х		\mathbf{X}^1		X^2		X^3	
Review prior & concomitant medication	Х	Х	Х	X	Х	Х	Х	Х	Х	Х
Query for AEs, SAEs, AESIs and NOCIs		Х	Х	X	X ^{1,f}	$X^{1,f}$	$X^{2,f}$	X ^{2,f}	X ^{3,f}	X ^{3,f}
Sample Collection Immunogenicity Assessments										
Serum		X ^{1,2,3,g}		X ^{1,2,3}		X ^{1,2}		X ^{2,3}		X ³
Whole blood (Flow Based)		X ^{1,2,3}	X ^{1,2,3}	X1	X ¹	X ²	X ²	X ³	X ³	
Whole blood (PBMC)		X ^{1,2,3}	X ^{1,2,3}	X1	X^1	X ²	X^2	X ³	X ³	
Nasal Swab (Sam Device)		X ^{1,2,3}		X ^{1,2,3}		X ^{1,2}		X ^{2,3}		X ³
Saliva Sample		X ^{1,2,3}		X ^{1,2,3}		X ^{1,2}		X ^{2,3}		X ³

AE, adverse vent; AESI, Adverse event of special interest; EOS, End of Study; ET, Early Termination (7.2); HCV, Hepatitis C Virus; HIV, Human Immunodeficiency Virus; NP, Nasopharyngeal; NOCI, New Onset of Chronic Illness; PBMC, peripheral blood mononuclear cells; SAE, serious adverse event.

¹ = Cohort 1; ² = Cohort 2; ³ = Cohort 3.

^a For women of childbearing potential. Test at Day 1 and at second dose (boost). Test can be serum or urine test.

^b Targeted.

^c If screening lab tests are performed within 2 days prior to dosing, no need to repeat at Day 1.

^d Assess eligibility to receive second dose. Participants with acute illness or new medical condition may be re-assessed, and if the condition resolves, have a delayed 2nd dose within 1 week of scheduled visit.

^e If participants are not eligible to receive their 2nd dose, they immediately enter the follow-up period.

^f AEs will only be collected for 4 weeks following each study drug administration.

^g An aliquot of serum collected at baseline will be stored for testing (e.g. Platelet Factor 4 [PF4] antibody ELISA) should an AESI related to blood clots be reported anytime during the study period.

Follow-Up Period							
		COHORT 1	COF	IORT 2	COHORT 3		
Study Day	Months 3, 4, Month 7 5, 6 (Wk 28)/ EOS		Months 4, 5, 6, 7	Month 8 (Wk 32)/EOS	Months 5, 6, 7, 8	Month 9 (Wk 36)/ EOS	
Telephone Visit	Х		Х		Х		
Visit Window (days)	±7	±7	±7	±7	±7	±7	
Query for SAEs, AESIs and NOCIs	Х	Х	Х	Х	Х	Х	
Sample Collection Immunoger	nicity Assessme	nts					
Serum		Х		Х		Х	
Whole blood (Flow Based)							
Whole blood (PBMC) ^a		Х		Х		Х	
Nasal Swab (Sam Device)		Х		Х		Х	
Saliva		Х		Х		Х	

AE, adverse event; AESI, Adverse event of special interest; EOS, End of Study; ET, Early Termination; HCV, Hepatitis C Virus; HIV, Human Immunodeficiency Virus; NP, Nasopharyngeal; NOCI, New Onset of Chronic Illness; PBMC, peripheral blood mononuclear cells; SAE, serious adverse event. ^a Optional.

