2.2. Background

Noroviruses are a leading cause of foodborne disease and outbreaks of gastroenteritis worldwide and are responsible for substantial morbidity, mortality, and healthcare costs (Bányai, 2018). The

virus affects people of all ages; however, the incidence of disease is higher in younger children and in adults \geq 65 years old (Lopman, 2016; Esposito, 2020). Noroviruses are highly infectious with major mode of transmission by fecal-oral spread, usually via contaminated food or water (Teunis, 2008; de Graaf, 2016; Gaythorpe, 2018). The incubation period of norovirus is 10-51 hours.

Noroviruses are genetically diverse viruses. Genogroups I, II and IV are human-transmitted. Genogroup I and II account for the majority of norovirus outbreaks (Vega, 2014). Each genogroup is further divided into genotypes based on the similarity of the amino acid sequence of the major viral capsid protein, VP1. Genotypes GI.1 and GII.4 represent the genogroups responsible for most outbreaks and the majority of the disease burden globally (Lopman, 2016).

Norovirus causes extensive morbidity with clinical symptoms of nausea, vomiting, non-bloody diarrhea, and abdominal cramps. Fever, headache, and body aches have been reported as well. These symptoms usually last 2-4 days. Additionally, asymptomatic infections are estimated to occur in approximately one-third of infected people. Currently no specific therapy exists for norovirus gastroenteritis. The standard treatment is oral rehydration with fluids and electrolytes (Glass, 2009). There are currently no licensed vaccines for norovirus.

Norovirus is an enteric pathogen and infects the epithelial cells of the small intestine. Vaxart's platform is based on oral delivery of the vaccine to the intestinal mucosa, which is analogous to the natural route of norovirus infection and entry. Human and animal experience with Vaxart's orally administered platform has demonstrated that substantial transgene specific intestinal IgA responses can be generated in addition to systemic IgG responses to the expressed antigen (influenza HA and norovirus VP1). These platform attributes may allow for better protection against norovirus infection than an injected protein-based vaccine.

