8.4. Adverse Events and Serious Adverse Events

The definitions of any AE (solicited and unsolicited), SAE and AESIs/NOCIs can be found in Appendix 3 (Section 10.3).

The investigator and any qualified designees are responsible for detecting, documenting, and recording events that meet the definition of any AE (solicited and unsolicited), or SAE. Investigators remain responsible for following up AEs, SAEs and other reportable safety events for outcome.

8.4.1. Time Period and Frequency for Collecting AE, SAE and Other Reportable Safety Event Information

All AEs (solicited and unsolicited), SAEs and other reportable safety events that occur after the consent form is signed but before study administration must be reported by the investigator if the event cause the participant to be excluded from the study or is the result of a protocol-specified intervention, including but not limited to washout or discontinuation of usual therapy, diet, or a procedure.

Table 5 below summarizes the different reporting timelines for AEs (unsolicited and solicited), SAEs, SUSAR and pregnancy.

Medical occurrences that begin before the start of study drug but after obtaining informed consent will be recorded on the Medical History/Current Medical Conditions section of the eCRF not the AE section.

All SAEs will be recorded and reported to the Sponsor or designee immediately and under no circumstance should this exceed 24 hours, as indicated in Appendix 3 (Table 17). The investigator will submit any updated SAE data to the Sponsor within 24 hours of it being available.

Table 5	Adverse	Event	Reporting	Timelines	to the	Sponsor

Type of Event	AE (unsolicited)	AE (solicited)	SAE / AESI / NOCI	Pregnancy
Reporting period	From first dose until 4 weeks after last dose of study drug	1 week after each study drug administration	From first dose until end of Follow-Up Period/ EOS	From first dose until end of Follow-Up Period/ EOS
Reporting Timelines to the Sponsor	Entered into the clinical database on an ongoing basis	Entered into the clinical database on an ongoing basis	Within 24 hours	Within 24 hours
Reporting Method	AE eCRF	Solicited Symptom Diary	AE eCRF or SAER Form	Pregnancy form

AE, Adverse event; SAE, Serious adverse event; SUSAR, serious unexpected suspected adverse reaction.

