- Unsolicited AEs are any AEs reported spontaneously by the participant, observed by the study personnel during study visits or those identified during review of medical records or source documents. Unsolicited AEs (all AEs not collected in the Solicited Symptom Diary during the first week following each study drug administration) will be monitored and collected from the time of each dose through 4 weeks post each dose.
- Solicited AEs are predefined systemic signs and symptoms of reactogenicity for which the participant is specifically questioned, and which are noted by the participant in their Solicited Symptom Diary, including:
 - fever (any temperature 100°F or higher)
 - headache
 - myalgia (muscle pain)
 - abdominal pain
 - anorexia (defined and not eating)
 - nausea
 - vomiting
 - diarrhea
 - malaise/fatigue

Participants will utilize a Solicited Symptom Diary issued on the day of each study drug administration to record solicited AE daily for the 1 week following each dose.

Table 8Events Meeting Definition of AE

Events Meeting the AE Definition

- Any abnormal laboratory test results (hematology, clinical chemistry, or urinalysis) or other safety assessments (e.g., vital signs measurements) that worsen from baseline and are considered clinically significant in the medical and scientific judgment of the investigator.
- Exacerbation of a chronic or intermittent pre-existing condition including either an increase in frequency and/or intensity of the condition.
- New conditions detected or diagnosed after study drug administration even though it may have been present before the start of the study.
- Signs, symptoms, or the clinical sequelae of a suspected intervention- intervention interaction.
- Signs, symptoms, or the clinical sequelae of a suspected overdose of either study intervention or a concomitant medication. Overdose per se will not be reported as an AE/SAE unless it is an intentional overdose taken with possible suicidal/self-harming intent. Such overdoses should be reported regardless of sequelae.

Events **NOT** Meeting the AE Definition

- Events that occurred from consent to pretreatment
- Medical or surgical procedure (e.g., endoscopy, appendectomy): the condition that leads to the procedure is the AE.
- Situations in which an untoward medical occurrence did not occur (social and/or convenience admission to a hospital).

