3.3 Study treatments and assessments

Subject participation will last for about 7 months for Cohort 1 (4-week boost vaccination), 8 and 9 months for Cohorts 2 and 3 respectively (Cohort 2: 8-week boost vaccination; Cohort 3: 12-week boost vaccination). Subjects will be followed for 4 weeks after each dose, and through 6 months following the boosting dose. Following confirmation of eligibility during the screening period, subjects will be enrolled and receive their first

dose of study vaccine on Day 1 and their second dose of study vaccine on Day 29, Day 57 or Day 85 depending on their assigned cohort if deemed eligible after pre-dose safety assessments.

Subjects will record any potential symptoms of reactogenicity daily for 1 week after each dose and return to the site to have safety assessments and samples collected for evaluation of immunogenicity. Subjects deemed ineligible for the second vaccination due to acute illness or new medical condition may be reassessed and have a delayed second vaccination within 1 week of their scheduled vaccination visit if the condition resolves. If a subject remains ineligible after the re-assessment, they will complete an Early Termination (ET) visit and then enter the scheduled follow-up period per cohort assignment as outlined in the schedule of events (SoE). All subjects will enter the follow-up period 4 weeks after their last vaccination and will be monitored for serious adverse events (SAEs), adverse events of special interest (AESIs) and new onset of chronic illness (NOCI) through the End of Study. Subjects will also have samples collected for evaluation of immunogenicity as scheduled in SoE.

A detailed description of procedures and assessments to be conducted during the active period of this study is summarized in the Schedule of Events in Table 2 below, with those during the follow-up period summarized in Table 3.

Table 2 – Schedule of Events (Active Period)

Active Period										
	Screen	Study Period	1 – Cohorts 1	, 2, 3						
				Stud	y Period 2 –	Cohort 1				
						Study Peri	od 2 – Cohor	t 2		
								Study Peri	od 2 – Cohort 3	
Study Day	-45d to -1 d	Day 1 (Wk 0)	Day 8 (Wk 1)	Day 29 (Wk 4)	Day 36 (Wk 5)	Day 57 (Wk 8) /ET ¹	Day 64 (Wk 9)	Day 85 (Wk 12)/ET ²	Day 92 (Wk 13)	Day 113 (Wk16)/ET ³
Visit Window (days)		n/a	0	±2	0	±2	0	±2	0	±2
Informed consent	Х									
Inclusion/Exclusion	Х	Х		Х						
Demographics	Х									
Medical history	Х									
Stool for occult blood	Х									

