7.2 Handling of missing data and outliers

The extent and pattern of missing data for primary, secondary, and exploratory endpoints will be summarized by cohort and visit date with frequencies and percentages. No imputations will be conducted for missing data other than dates. No outliers will be eliminated.

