8.6.1.1 Responder Analysis

A responder analysis at each appropriate post-dose follow-up visit (see Table 1 and Table 2 for specific timings) will be conducted for the Norovirus G1.1 HBGA BT50. During active period, the numbers and percentages (with 95% CIs) of subjects with a ≥ 2 -, 3- or 4-fold increase from baseline antibody levels will be summarized, respectively. Durability of immune responses will be evaluated using the safety follow-up period samples collected at 6 months post the second dose (Month 7 for Cohort 1, Month 8 for Cohort 2, and Month 9 for Cohort 3). Numbers and percentages of subjects with a ≥ 2 -, 3- or 4-fold increase from baseline antibody levels at both 28 day post the second dose (Day 57 for Cohort 1, Day 85 for Cohort 2, and Day 113 for Cohort 3) and 6 month post the second dose will be summarized, where percentages will be calculated as of the number of subjects with a ≥ 2 -, 3- or 4-fold increase from baseline antibody levels at 28 day post the second dose will be summarized, where percentages will be calculated as of the number of subjects with a ≥ 2 -, 3- or 4-fold increase from baseline antibody levels at 28 day post the second dose. Fisher's exact test will be used to compare the percentages of responders for each category among cohorts.

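### Natural norovirus infection in the 140 days before End of Study is not asked about and has no analysis rule, so an antibody rise from it would count as durable vaccine response

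*Protocol*

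**What the plan says.** **Recording of illness.** Footnote f of the Schedule of Activities (Protocol 1.2) states that "AEs will only be collected for 4 weeks following each study drug administration". Protocol 8.2 gives the same window, and so does the definition of unsolicited events in Appendix 3, Table 7, where they "will be monitored and collected from the time of each dose through 4 weeks post each dose". Table 5 in Protocol 8.4.1 differs: it sets one continuous reporting period, "From first dose until 4 weeks after last dose of study drug". In the Follow-Up Period table the only event row is "Query for SAEs, AESIs and NOCIs". Acute gastroenteritis is not on the AESI list in Appendix 5.

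**Analysis.** SAP 8.6.1.1 says: "Durability of immune responses will be evaluated using the safety follow-up period samples collected at 6 months post the second dose". The durability percentage is the share of participants with a 2-, 3- or 4-fold BT50 rise at 28 days post-boost who still have it at 6 months. Both rises are measured from the initial baseline. The ANCOVA in SAP 8.6.1.2 adjusts for baseline log titre only, and SAP 7.2 adds "No outliers will be eliminated".

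**Natural infection.** Protocol 2.2 notes that "asymptomatic infections are estimated to occur in approximately one-third of infected people". Neither document schedules a norovirus test. Neither names norovirus infection as a deviation, a reason for exclusion or the subject of a sensitivity analysis (SAP 6.3, 6.4 and 8.6).

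**The concern.** BT50 and VP1 serum IgG measure antibody to GI.1 antigen, and an infection with GI.1 or a cross-reactive strain can be expected to raise them as the vaccine does. The protocol itself describes norovirus as a leading cause of gastroenteritis at all ages. If a participant is infected after the 28-day post-boost sample, the End of Study titre mixes vaccine durability with natural boosting. An ordinary episode would leave no record, because it is neither serious nor on the AESI list nor a chronic illness.

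At stake is the 6-month durability result. The denominators are small, so one re-boosted participant can make waning look slower. Without a rule set beforehand, a late rise would be explained or ignored after the data are seen, in an open-label study.

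**Working it through.** The plan gives no sample-size calculation and no incidence, so there is no figure of its own to reproduce.

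**1. Days without collection of non-serious events, under footnote f**
- Boost days come from SAP 3.3: "second dose of study vaccine on Day 29, Day 57 or Day 85 depending on their assigned cohort". The 28-day post-boost visits are Weeks 8, 12 and 16; End of Study is Weeks 28, 32 and 36.
- Follow-up gap: 28 − 8 = 32 − 12 = 36 − 16 = 20 weeks = 140 days in every cohort (nominal, ignoring visit windows).
- Pre-boost gap: boost day minus Day 29 = 0, 28 and 56 days in Cohorts 1, 2 and 3.
- Under Table 5 the pre-boost gap is 0, 0 and 0 days. The follow-up gap stays at 140 days.

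**2. Effect of one participant on durability**
- Responder numbers are illustrative. Protocol 2.2 reports 78% with a 2-fold rise in one prior study (high-dose group, single immunization) and 43% with a 4-fold rise in another. Applied to 10 participants these give about 8 and 4 responders.
- One participant changing status moves the rate by 1/8 = 12.5 points or 1/4 = 25 points.

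**3. Effect of one infection on a geometric mean of 10**
- An extra f-fold rise in one of 10 multiplies the cohort geometric mean by f^(1/10): 4^0.1 = 1.15, 10^0.1 = 1.26, 30^0.1 = 1.41. These apply only if an infection occurs.

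**4. How many infections before End of Study**
- Assumption, not in the documents: 2% to 20% a year of infections that raise GI.1 titres.
- All 30 participants: 30 × 140/365.25 = 11.5 person-years, so 0.23 to 2.30 expected; chance of at least one, 1 − exp(−expected), 21% to 90%.
- Only 28-day responders can enter the durability percentage:
  - 4 per cohort (12 in all): 12 × 140/365.25 = 4.6 person-years, 0.09 to 0.92 expected, 9% to 60% chance of at least one.
  - 8 per cohort (24 in all): 9.2 person-years, 0.18 to 1.84 expected, 17% to 84%.
- Only those who would otherwise have fallen below the threshold change status, so these figures are upper bounds on status changes.

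**5. How many before the boost, taking footnote f as it stands**
- Cohort 2: 10 × 28/365.25 = 0.77 person-years, 0.02 to 0.15 expected, 1.5% to 14% chance of any.
- Cohort 3: 10 × 56/365.25 = 1.53 person-years, 0.03 to 0.31 expected, 3% to 26%.
- Average effect on Cohort 3's geometric mean for a 10-fold rise: 10^(0.031/10) = 1.007 to 10^(0.307/10) = 1.073, or about 0.7% to 7%.

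**The case against.** A reader might infer that infection goes unrecorded between the doses and so favours the longer schedules. The documents do not support that as a settled conclusion. Table 5 would collect unsolicited events throughout that interval. Concomitant medication with its reason is recorded through the active period (Protocol 6.5), acute illness is assessed at the boost visit, and a hospitalised case is an SAE at any time. Even under footnote f, the single most likely number of infections in Cohort 3 before the boost is zero across the whole assumed range. IgA ASC, the first-listed primary endpoint, is sampled on the dose day and 7 days later, so it is probably little exposed.

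A reader might also infer that the follow-up gap favours one schedule. It is 140 days in every cohort, so its length does not. Calendar time could differ because Cohorts 3 and 2 may be enrolled first (Protocol 4), but the documents give nothing with which to size that.

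It is also fair to say that the data will be on display. SAP Table 4 defines change from previous visit, results are summarised by visit, and all subject data are listed (SAP 8.1), so a late rise could be seen. The trial is small, non-randomised and has no formal sample-size calculation.

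These arguments narrow the point mainly to durability. They do not remove it: Table 5 stops 4 weeks after the last dose, a listing is not a rule, and asymptomatic infections escape any symptom-based record.

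**Conclusion.** The concern holds for the 6-month durability analysis. Non-serious gastroenteritis is not queried for 140 days, and nothing in the SAP separates a natural GI.1 rise from vaccine response. One infected 28-day responder who would otherwise have waned moves a cohort's durability rate by 12.5 to 25 points, if there are 8 or 4 responders. The chance that any 28-day responder is infected in that window is 9% to 84% across the two illustrative responder numbers and the assumed 2% to 20% a year. That range is wide because the documents give no incidence, and only GI.1 or cross-reactive infections count.

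Before the boost, the secure finding is a contradiction: footnote f, Protocol 8.2 and Appendix 3 leave 0, 28 and 56 days uncovered, Table 5 leaves none, and the passages must be reconciled. Any resulting bias would run towards the longer intervals through BT50 and serum IgG, but its expected size is small.

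This is a cheap improvement to a supportive result rather than a flaw that undermines the trial.

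**What to change.** 1. **SAP 8.6.1.1, durability.** Flag any participant whose BT50 or VP1 IgG rises at least 4-fold from 28 days post-boost to End of Study. Report the number by cohort, and repeat the durability analysis without them as a named, supportive sensitivity analysis.
2. **Remaining follow-up calls and the End of Study visit.** Add one question: any acute gastroenteritis since the last contact, with the date.
3. **Before the boost.** In Cohorts 2 and 3, report descriptively how many have a 4-fold rise from Day 29 to the boost-day serum. Do not base the cohort comparison on excluding them. Cohort 1 has no dose-free interval, so the exclusion would remove high risers, including late responders to the first dose, from Cohorts 2 and 3 only.
4. **Protocol.** Reconcile footnote f, section 8.2 and Appendix 3 with Table 5.

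The cost is a paragraph in the SAP, one extra analysis on sera already scheduled and one question at existing contacts. Protocol Appendix 7 reports enrolment complete with participants in safety follow-up, so a new question at the boost visit may come too late, but the serum flag remains feasible. Follow-up results are reported in an addendum (SAP 8.8), so the rule can be fixed before those data are analysed.

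The downside is that the flag uses a post-baseline value and misses an infection that only offsets waning, while the question misses asymptomatic infection and cannot identify the pathogen. The analysis is supportive only.
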